11.3.2 Hospitalizations

Hospitalizations are collected in the Hospitalization Records Form of the eCRF. For each subject, an entry will be recorded for each hospitalization. The days of hospitalization will be calculated as the sum of all hospitalizations durations in days (Date of discharge – Date of Admission + 1). In case of missing dates, the hospitalization duration will be assumed to be 5 days.

Only hospitalizations with admission dates that occur during the Treatment Period and up to 7 days after the last study medication date will be taken into account.

The following hospitalization-related data will be analyzed and compared between the 2 treatment groups:

- Time to first hospitalization (% of subjects) up to Week 52, 7 days after last dose.
- Time to first hospitalization or skilled nursing facility (% of subjects) up to Week 52, 7 days after last dose.
- Number of days of hospitalizations
- Number of days of medical-facility
- Number of days of hospitalizations per patient-exposure year (PEY).
- Number of days in hospital or skilled nursing facility per patient-year exposure (PEY).
- Number of days of medical-facility (hospital, skilled nursing facility, emergency room, or overnight observation) per subject-exposure year (PEY).
- Number of days on treatment out of hospital and skilled nursing facility up to Week 52, 7 days after Last Dose.

Note: Sensitivity analysis may be performed by excluding elective procedures using only hospitalization due to AE

The time to hospitalization event will be compared between the two treatment groups using cox model including baseline stratification factors. The proportion of subjects hospitalized will be compared between the 2 treatment groups using logistic regression model and stratified by the baseline stratification factors. The mean number of days of hospitalization will be analyzed and compared between the 2 treatment groups using the Mantel-Haenszel mean score test adjusting for stratification factors.

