## 4 STUDY DESIGN

### 4.1 Description of the Study

This open-label, randomized, active controlled study is designed to evaluate the efficacy and safety of roxadustat compared to epoetin alfa for the maintenance of hemoglobin (Hb) levels in subjects on HD or PD or HHD originally on ESA for treatment of anemia.

- **Screening Period:** Up to 6 weeks. For subjects currently taking Mircer®, the Screening Period can be extended up to 8 weeks
- **Treatment Period:** Treatment duration is variable for individual subjects, with a minimum treatment duration of 52 weeks and a maximum duration of up to approximately 3 years after the last subject is randomized

**Amendment 1& 2:** In order to complete the Phase 3 program in a timely manner, minimum treatment duration of subjects enrolled under Amendment 1 & 2 may be shortened. Subjects will be informed at least 4 weeks in advance if such decision is made. All active subjects will end the study at the same time

- **Post-Treatment Follow-Up Period:** 4 weeks

During the course of the study, visits and assessments will be performed as defined in the schedule of assessments.

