### **8.3.5 Reporting Serious Adverse Events on the SAE Report Form**

All SAEs must be reported immediately to the Sponsor and/or its designated safety management vendor.

To report an SAE, the investigator must fax an SAE Report Form to Sponsor's designated safety management vendor within 24 hours of becoming aware of the serious event. In case of emergency or doubt, the Investigator shall call Sponsor's Medical Monitor for guidance. Follow-up reports must be submitted in a timely manner as additional information becomes available.

Full details of the SAE should also be recorded on the medical records and onto the eCRF. The following minimum information is required:

- Subject number, sex and age
- The date of report
- A description of the SAE (event, seriousness of the event)
- Causal relationship to the study drug

Follow-up information for the event should be sent promptly (within seven days) as necessary.

For each SAE observed, the investigator should obtain all of the information available about the event, including (but not limited to): hospital discharge diagnoses, hospital discharge note, death certificate, appropriate laboratory findings (including autopsies and biopsy results), and clinical examinations (including radiological examinations and clinical consultations).

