4.3 Additional Evaluation of Efficacy

The additional efficacy evaluations in this study are:

- **Hemoglobin Maintenance:**
 - Hemoglobin long-term Maintenance: Mean change from baseline in hemoglobin averaged over 8 weeks of treatment at Weeks 44-52 without

- rescue therapy within 6 weeks prior to and during this 8-week evaluation period.
- Mean change from baseline in hemoglobin averaged over the Week 96 to 104 of treatment, without rescue therapy within 6 weeks prior to and during this 8-week evaluation period.
 - Change from baseline in hemoglobin at each of the selected post-dosing time points.
 - Proportion of subjects with Hb ≥ 10 g/dL averaged over Weeks 28 to 36, 44 to 52, and 96 to 104 of treatment without rescue therapy within 6 weeks prior to and during the evaluation periods.
 - Proportion of subjects with Hb ≥ 10 g/dL averaged over Weeks 28 to 36, 44 to 52, and 96 to 104 of treatment regardless of rescue therapy
 - Proportion of subjects with Hb within 10-12 g/dL averaged over Weeks 28 to 36, 44 to 52, and 96 to 104 of treatment without rescue therapy within 6 weeks prior to and during these 8-week evaluation periods.
 - Proportion of subjects with Hb within 10-12 g/dL averaged over Weeks 28 to 36, 44 to 52, and 96 to 104 of treatment regardless of rescue therapy use.
 - Hemoglobin change from baseline to the average hemoglobin value of weeks 28 to 36, 44 to 52, and 96 to 104 of treatment regardless of the use of rescue therapy.
- **Iron Supplement:**
 - Time to and Proportion of subjects who has requirement for IV iron supplementation.
 - Mean monthly IV iron (mg) per subject during weeks 28-52, 53-104, and 105 -EOT.
 - Mean monthly oral iron (mg) use per subject during 28-52, 53-104, and 105 - EOT.
 - Proportion of subjects who has Requirement for only oral iron supplementation (Week 1 to 52).
 - **Hospitalizations**
 - Time to first hospitalization (% of subjects) up to Week 52, 7 days after Last Dose. Time to first hospitalization or skilled nursing facility (% of subjects) up to Week 52, 7 days after Last Dose.
 - Number of days of hospitalizations due to AE per subject-exposure year (PEY)
 - Number of days in hospital or skilled nursing facility due to AE per patient-year exposure (PEY)
 - Number of days in medical-facility (hospital, skilled nursing facility, emergency room, or overnight observation) due to AE per patient-year exposure (PEY)

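### The flat 5-day rule for hospital stays with a missing date ignores a known death or end-of-observation date: it shortens stays still open at EOS and misstates in-hospital deaths in either direction

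*SAP*

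**What the plan says.** SAP 11.3.2 sums stay lengths computed as "Date of discharge – Date of Admission + 1". The fallback is one sentence: where dates are missing, "the hospitalization duration will be assumed to be 5 days". It does not separate a missing discharge date from a missing admission date or a partial date, and it gives no basis for the figure of 5.

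Stays are selected by admission date: "Only hospitalizations with admission dates that occur during the Treatment Period and up to 7 days after the last study medication date" are counted. The formula does not cut the stay itself at that limit.

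The day counts are compared between arms: "The mean number of days of hospitalization will be analyzed and compared between the 2 treatment groups using the Mantel-Haenszel mean score test". SAP 4.3 lists the hospital-day outcomes among the additional efficacy evaluations. None of them is in the fixed sequence of SAP Table 6.

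No other section supplies a rule for hospitalization dates. SAP 16.5.2 covers adverse event dates and 16.5.3 medication dates. SAP 16.5.4 imputes the last dose date as the earliest of several candidates, including the dates of death and of the EOT/EOS visit, but it applies to the last dose date only.

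**The concern.** Two kinds of stay can lack a discharge date although their length is known or bounded: one that ends in death, and one still in progress when observation stops. Stays of the second kind are foreseeable, because for subjects enrolled under Amendments 1 and 2 Protocol 4.1 says "All active subjects will end the study at the same time". The 5-day rule replaces usable information in both cases.

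The information should often be on file. Protocol 8.3.5.2 requires every death during participation to be reported and an eCRF completed. Protocol 8.3.5 asks sites to obtain, for each SAE, the "hospital discharge diagnoses, hospital discharge note, death certificate" and other records. SAP 16.5.4 already applies the bounding principle to the last dose date, so hospital stays are handled inconsistently with the SAP's own practice.

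At stake is the accuracy of total hospital days, days per patient-exposure year, the hospital part of the nursing-facility and medical-facility counts, and days on treatment out of hospital. These are compared between arms in an open-label trial, so the rule is best settled before analysis.

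**Working it through.** **The plan's own figure.** The 5 days is a convention with no stated derivation, so there is nothing to reproduce.

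**Which date is likely to be missing.** A stay qualifies by its admission date, and that filter cannot be applied reliably without one. For a stay confirmed as countable, the missing item is therefore mainly the discharge date.

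**Stay still open at EOS.** Inputs: admission no later than 7 days after last dose (SAP 11.3.2); EOS 15 to 31 days after last dose (SAP Table 11).

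Minimum length = EOS day − 7 + 1. Minimum understatement = minimum length − 5.

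| EOS, days after last dose | Minimum length | Counted | Understated by at least |
|---|---|---|---|
| 15 | 15 − 7 + 1 = 9 | 5 | 4 |
| 21 | 15 | 5 | 10 |
| 28 | 22 | 5 | 17 |
| 31 | 25 | 5 | 20 |

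The sign is certain in every row.

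**Death in hospital, discharge date blank.** If the patient dies on stay day L, the true length is L and the error (imputed minus true) is 5 − L.

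| Stay day of death | 1 | 2 | 3 | 4 | 5 | 7 | 10 | 14 | 21 |
|---|---|---|---|---|---|---|---|---|---|
| Error, days | +4 | +3 | +2 | +1 | 0 | −2 | −5 | −9 | −16 |

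For deaths on days 1 to 4 the rule records hospital days after the patient has died.

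**Net direction for deaths.** The documents give no length-of-stay data. As an assumption only, take a geometric length with mean m. Then P(overstated) = 1 − (1 − 1/m)^4, P(understated) = (1 − 1/m)^5, and mean error = 5 − m.

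| Assumed mean stay m, days | Overstated | Understated | Mean error, days |
|---|---|---|---|
| 3 | 80% | 13% | +2 |
| 5 | 59% | 33% | 0 |
| 8 | 41% | 51% | −3 |
| 14 | 26% | 69% | −9 |

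The sign of the net error changes within this range.

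**The case against.** The best defence is that the rule is a fallback for the little that stays missing. Protocol 8.3.5 has sites seek discharge notes and death certificates, and Protocol 13.2 says incomplete data will be queried. The documents do not say how the Hospitalization Records Form codes a stay that ends in death; if sites enter the death date as the discharge date, the ordinary formula applies and the problem does not arise. An open stay at EOS must also be long, at least 22 days if EOS falls on day 28, and nothing shows that such stays are common. All of this stands and limits how often the rule bites. It does not supply the missing exception.

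The reach is also limited. Days on treatment out of hospital stops at Week 52, while original-protocol subjects have a planned minimum of 52 weeks, so a stay open at their closeout would generally fall outside that outcome. The SAP does not say whether the rule extends to nursing-facility or emergency-room stays.

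A further objection concerns the obvious remedy of ending every stay without a discharge date at last contact or data cut-off. Such a date nearly always exists, so a discharge date that was simply never retrieved would become an enormous stay. Admission at Week 10 with last contact at Week 100 would count (100 − 10) × 7 + 1 = 631 days. This is right, and the fix below is restricted accordingly.

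**Conclusion.** The gap is real and minor. The rule understates every qualifying stay still open at EOS, by at least 4 days per stay at the earliest EOS day in the SAP window. It misstates in-hospital deaths in either direction unless death falls on stay day 5. The first result assumes that observation runs to an EOS at least 15 days after last dose; if it ended earlier, the bound is shorter. The second assumes that the discharge date is left blank at death.

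A reader might infer that hospital days are generally understated, or by a particular percentage. The documents do not support that. Suppose 5% of stays are affected and the others average 6 days. If the affected stays truly average 15 days, the true mean is 0.95 × 6 + 0.05 × 15 = 6.45 and the recorded mean 0.95 × 6 + 0.05 × 5 = 5.95, which is 7.8% too low. If they average 3 days, the true mean is 5.85 and the recorded mean 1.7% too high. The share and all the lengths are assumptions.

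Nor do the documents show that stays without a discharge date are mostly deaths or ongoing stays, or that the rule shrinks or favours any difference between arms. The primary endpoint and the fixed-sequence tests are untouched, and time to first hospitalization does not use stay length.

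**What to change.** Replace the single sentence in SAP 11.3.2 with an ordered rule:

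1. Admission date known, discharge date missing, patient died during that stay: end the stay at the date of death.
2. Admission date known, discharge date missing, stay recorded as ongoing at last contact or EOS: end the stay at that date.
3. Any other case, meaning a discharge date not retrieved or an admission date missing: keep 5 days, but never let the imputed stay run past death or the end of observation.

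Report the number of imputed stays per arm, ideally by case.

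A missing admission date should not be filled from the onset of a related SAE: neither document describes a link between hospitalization records and SAE records.

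The cost is a few lines of SAP text and a little more derivation work. No new data collection is evident, but the team should confirm how the Hospitalization Records Form marks death and ongoing stays, since the documents do not say.

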### 3.2.3 Additional Evaluation of Efficacy

The additional efficacy evaluations in this study are:

- Hb Maintenance:
  - Hemoglobin Long-Term Maintenance: Mean change from BL in Hb averaged over 8 weeks of treatment at Weeks 44 to 52 without rescue therapy within 6 weeks prior to and during this 8-week evaluation period
  - Mean change from BL in Hb averaged over the final 8 weeks of treatment, without rescue therapy within 6 weeks prior to and during this 8-week evaluation period
  - Change from BL in Hb at each of the selected postdosing time points
  - Proportion of subjects with 10-12 g/dL averaged over Weeks 28 to 36, 44 to 52, and the final 8-weeks of treatment without rescue therapy within 6 weeks prior to and during this 8-week evaluation period
  - Hb response during Weeks 28 and 36 regardless of use of rescue therapy
  - Hb change from BL to the average Hb value of Weeks 28 to 36, 44 to 52, and the final 8 weeks of treatment regardless of the use of rescue therapy
- Iron Supplement:
  - Requirement for IV iron supplementation
  - Mean monthly IV iron (mg) per subject during Weeks 37 to 52 and Week 53 to EOS
  - Mean monthly oral iron (mg) use per subject during Weeks 1 to 36, Weeks 37 to 52, and Weeks 53 to EOS
  - Requirement for only oral iron supplementation
- Hospitalizations:
  - Occurrence (number) of hospitalizations
  - Proportion of subjects hospitalized
  - Number of days of hospitalizations per patient-exposure year (PEY)

- Missed Dialysis:
  - Occurrence (number) of missed dialysis sessions
  - Proportion of subjects with missed dialysis sessions
  - Number of days of missed dialysis sessions per patient-exposure year (PEY)
- Rescue Therapy Use:
  - Proportion of subjects who receive RBC transfusions
  - Number of RBC packs per patient-month exposure to study medication
  - Having received rescue therapy [composite of RBC transfusions and rescue ESA]
- Changes in Cholesterol Levels:
  - Change from BL at each of the selected treatment time points in:
    - Total cholesterol
    - Low-density lipoprotein/high-density lipoprotein ratio
    - Non-HDL cholesterol
  - Proportion of subjects achieving LDL target of < 100 mg/dL averaged over Weeks 12 to 28 of treatment
- Blood Pressure Effect:
  - Proportion of subjects achieving BP treatment goal in ESRD subjects (predialysis systolic BP < 140 mmHg and diastolic BP < 90 mmHg) averaged over Weeks 12 to 28
  - Time to a treatment-emergent AE of hypertension

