##### 4.6.3.2 Erythropoiesis Stimulating Agents

For subjects randomized to roxadustat the use of ESAs is generally prohibited. Erythropoiesis stimulating agent rescue is restricted to no more than one cycle of use during the Treatment Period; the Investigator may initiate use of an approved EPO analogue if all of the following criteria are met:

- A subject's Hb level has not sufficiently responded to two or more dose increases or the maximum dose limit of the study drug has been reached; and
- The subject's Hb is  $<$  8.5 g/dL on two consecutive measurements (central lab) drawn at least five days apart; and
- Clinical judgment does not suggest iron deficiency or bleeding as a cause of lack of response or rapid decline in Hb; and
- Reducing the risk of alloimmunization in transplant eligible patients and/or reduction of other RBC transfusion-related risks is a goal

The subject is not allowed to be administered both the EPO analogue and roxadustat at the same time. Treatment with an EPO analogue should be started  $\geq$  3 days after the last dose of roxadustat, and should be stopped when Hb  $>$  9 g/dL or after 4-weeks, whichever comes first. If a subject requires longer than 4-weeks therapy due to inadequate response the Medical Monitor should be contacted. Study treatment should be resumed after the following intervals:

- Two days after stopping epoetin
- One week after stopping darbepoetin alfa
- Two weeks after stopping methoxy polyethylene glycol-epoetin beta (Mircera®)

If more than one cycle of EPO analogue rescue is required, the Investigator should permanently discontinue roxadustat. Use of EPO analogues will be recorded in the eCRF.

Inadvertent ESA administration or ESA administration by the hospital staff in Roxadustat subjects should not be counted as rescue unless above criteria are met; these subjects may be allowed to continue taking study medication, if considered safe by the Investigator or Medical Monitor.

For subjects randomized to epoetin alfa, the Investigator may initiate use of a different EPO analogue if clinically indicated. Use of the different EPO analogue will be recorded in the eCRF and will be considered rescue therapy.

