11.3.3.1 Red Blood Cell Transfusion

For a subject receiving RBC or whole blood transfusion, the Time at Risk (time up to first use) will be calculated (in years) as:

$$(\text{First use of transfusion date} - \text{First dose date of study medication} + 1) / 365.25$$

For a subject not receiving transfusion, the Time at Risk (time until they get censored) is calculated as:

$$(\text{Date of last study medication} - \text{First dose date of study medication} + 1) / 365.25$$

The red blood cell transfusion form of the eCRF in the cumulative visit will be used to derive the number of RBC packs. The number of RBC units is collected in this form. For transfusions where the number of units is not given but the volume transfused is given, the number of units will be estimated by dividing the volume transfused by 250 mL (for transfusion of packed cells) or by dividing the volume transfused by 500 mL (for transfusion of whole blood).

The total number of RBC units/packs during the Treatment Period is calculated for each subject by the sum of the transfused units between the Analysis Date of First Dose and up to the Analysis Date of Last Dose. The following 2 endpoints will be analyzed:

- Proportion of subjects who receive RBC transfusions. The proportion of subjects who received RBC transfusion will be compared between the 2 treatments using logistic regression model adjusting for baseline hemoglobin as covariate and treatment group and stratification factors as fixed effects.
- Number of RBC packs per subject-month exposure to study medication. The mean number of RBC packs will be compared between the 2 treatment groups using ANCOVA model adjusting for baseline hemoglobin as covariate, treatment group, and stratification factors as fixed effects.

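### Hospital days, missed-dialysis days and RBC packs are declared per unit of exposure, but the only comparisons written use per-subject totals with no exposure term

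*SAP*

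**What the plan says.** **Declared endpoints.** Protocol 3.2.3 lists hospital days and missed-dialysis days per patient-exposure year (PEY), and RBC packs per patient-month of exposure. SAP 4.3 repeats all three, limiting the hospital version to admissions due to adverse events. SAP 11.3.2 lists hospital days as a plain number and also per PEY, with further per-PEY items for skilled nursing and for any medical facility.

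**Written comparisons.**
- Hospital days (SAP 11.3.2): "The days of hospitalization will be calculated as the sum of all hospitalizations durations in days". The one test for days is: "The mean number of days of hospitalization will be analyzed and compared between the 2 treatment groups using the Mantel-Haenszel mean score test", adjusted for stratification factors.
- Missed-dialysis days (SAP 11.3.3): under the per-PEY item, mean days are compared by the same kind of mean score test.
- RBC packs (SAP 11.3.3.1): a total is defined for each subject from first to last dose. Then, under the per-subject-month item: "The mean number of RBC packs will be compared between the 2 treatment groups using ANCOVA model", with baseline hemoglobin, treatment and strata.

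**Counting windows.** For hospital stays: "Only hospitalizations with admission dates that occur during the Treatment Period and up to 7 days after the last study medication date" count. Missed dialyses use the same 7-day tail. RBC units stop at the last dose. SAP section 3 makes treatment duration variable, up to about 3 years after the last subject is randomized. SAP 9.1 defines PEY as last dose date minus first dose date plus 1.

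**Missing hospital dates** (SAP 11.3.2): "In case of missing dates, the hospitalization duration will be assumed to be 5 days".

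**The concern.** A total collected only while a subject is on drug depends on two things: how often events occur, and how long the subject stays on drug. The endpoints as declared divide by exposure and so separate the two. The comparisons as written do not. A programmer following the text would either run a test on totals or have to guess that a rate was meant. Where the SAP does mean a rate it can say so: the IV iron analysis in SAP 11.2.2.4 divides milligrams by days over 28.

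Differential exposure is plausible here. For roxadustat, Protocol 4.6.3.2 says: "If more than one cycle of EPO analogue rescue is required, the Investigator should permanently discontinue roxadustat". The same section lets investigators switch epoetin subjects to another EPO analogue and sets no matching stopping rule for them. The trial is open-label.

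At stake is a nominal p-value on resource use that credits one arm with fewer hospital days or fewer packs when it was only observed for less time.

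**Working it through.** **1. The plan's own figures.** The plan gives no design figure for these endpoints. Its only power figure is for the primary hemoglobin endpoint (SAP 5.1: at least 99% with 600 subjects). With 300 per arm, distance to the margin is 0.75 − 0.30 = 0.45, the standard error is 1.25 × √(2/300) = 0.102, and power is Φ(0.45/0.102 − 1.96) = 0.993. It reproduces, but has no bearing on this point.

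**2. Expected totals at equal rates.** Let λ be a common rate, T0 the mean exposure in the longer-exposed arm and r the exposure ratio.
- RBC packs (counted to last dose): ratio of mean totals = λrT0 / λT0 = r.
- Hospital and missed-dialysis days (7-day tail, w = 7/365.25 = 0.0192 years): ratio = (rT0 + w) / (T0 + w).

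The documents give neither T0 nor r. With T0 assumed at 1.0 to 2.0 years:

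| Assumed exposure ratio r | RBC pack ratio | Hospital-day ratio | Spurious reduction |
|---|---|---|---|
| 0.95 | 0.95 | 0.950–0.951 | about 5% |
| 0.90 | 0.90 | 0.901–0.902 | about 10% |
| 0.80 | 0.80 | 0.802–0.804 | about 20% |

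Example at T0 = 1.5, r = 0.80: (1.2 + 0.0192)/(1.5 + 0.0192) = 0.803. The tail barely softens the effect.

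**3. Effect on the test.** This is a null simulation with equal true rates and 2,000 trials per setting (Monte Carlo standard error about 0.5 percentage points at a 5% rate). All inputs are assumptions: mean exposure 1.5 years in the longer arm; 1.0 to 1.5 admissions a year with mean stay 7 days and between-subject overdispersion; 0.12 transfusion episodes a year with mean 2 packs. An unstratified two-group comparison of mean totals stands in for the planned mean score test and ANCOVA. Two-sided rejection rates at nominal 5%:

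| Exposure ratio | Hospital days, 300/arm | Hospital days, 600/arm | RBC packs, 300/arm | RBC packs, 600/arm |
|---|---|---|---|---|
| 1.0 | 5–6% | 5–6% | 5% | 5% |
| 0.9 | 10–12% | 15–21% | 7% | 7% |
| 0.8 | 29–35% | 47–62% | 12% | 18% |

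The excess over 5% favours the arm with less exposure. A rate comparison on the same data (total events over total exposure, same window in numerator and denominator) gave a median ratio of 0.98 to 1.01 and rejected in 4.6% to 6.1% of trials across every exposure ratio tried, down to 0.7.

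**4. Denominator.** PEY as written in SAP 9.1 is a number of days, with no division by 365.25, and leaves out the 7-day tail over which hospital stays and missed dialyses are counted.

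**5. Missing hospital dates.** The 5-day rule does not distinguish a missing discharge date from both dates missing. A subject admitted on Day 100 who dies in hospital on Day 130 with no discharge date recorded scores 5 days, against 130 − 100 + 1 = 31.

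**The case against.** Several points on the other side are sound.

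- **Raw hospital days are a listed item.** The mean score test in SAP 11.3.2 fits that item as written. The gap is that the per-PEY items beside it have no test; a reader might infer that the wrong test was attached to them, and the text does not go that far.
- **The RBC sentence is ambiguous.** It sits under the per-month item and may loosely mean packs per month. But no such variable is defined, only a total.
- **A reader might infer that unequal exposure is built in by the roxadustat stopping rule.** The documents do not support that. Variable treatment length alone is balanced by randomization; only differential discontinuation biases totals. A first rescue cycle already requires all four criteria in Protocol 4.6.3.2, how many subjects would need a second is not stated, and lack of efficacy is a discontinuation reason in either arm (Protocol 5.3).
- **Other analyses handle follow-up.** Time to first RBC transfusion is in the fixed sequence by Cox model, and time to first hospitalization is also analysed by Cox. Days on treatment out of hospital to Week 52 run the other way: shorter treatment looks worse. Discontinuation and exposure are reported by arm.
- **The 5-day rule is a separate matter.** It applies to both arms, the frequency of missing dates is unknown, and the 31-day case is a constructed extreme.

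What remains is that neither the per-exposure hospital items, nor the missed-dialysis item, nor the pack item has a comparison on the declared scale. The Cox models address first events only, not total days or packs.

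**Conclusion.** The point holds as a mismatch between declared endpoints and written comparisons. Followed literally, the SAP compares totals that shrink when drug stops early. If exposure differs between arms, equal rates produce an apparent reduction roughly equal to the exposure shortfall: about 5% to 20% for assumed ratios of 0.95 to 0.80. The inflation of false positives is marked for hospital days and modest for packs, under the rates assumed above. With equal exposure there is no bias.

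The documents establish neither the size nor the direction of any exposure difference, so it would be wrong to conclude that the plan favours roxadustat. Nor does the point reach the main conclusions: these are additional endpoints outside the fixed sequence (SAP 11.2.1) and without multiplicity adjustment (SAP 5.3). It should be corrected because the remedy is cheap and the declared endpoints currently cannot be programmed without guessing.

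**What to change.** - For each per-exposure endpoint (hospital days and the related facility items, missed-dialysis days, RBC packs), name the analysed variable and a rate analysis. One option is a negative binomial model with log exposure as offset, treatment and stratification factors, reporting the rate ratio and 95% CI. A ratio of totals with a robust standard error would also do.
- Keep per-subject totals, including raw hospital days, as descriptive summaries.
- Match the denominator to the counting window: first to last dose for packs; first dose to 7 days after last dose for hospital stays and missed dialyses. Write PEY with the division by 365.25.
- For missing hospital dates, use the date of death as the end of stay only when the admission date is known and the subject died during that stay. Otherwise keep the 5-day default and add a sensitivity analysis. Do not set discharge at last contact or data cut-off: a living subject admitted on Day 100 and last contacted on Day 800 would score 800 − 100 + 1 = 701 days.

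The cost is SAP wording and standard programming. No new data are needed.
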